4.1.4 Dose Escalation and Safety Committee

A DESC consisting of sponsor representatives and investigators will convene once a dose level cohort completes the DLT observation period and data are available for review. Refer to [Section 10.4.1 Dose Escalation and Safety Committee] and DESC charter for additional details.

The DESC will also review the aggregate safety data from the phase 1 dose escalation and the phase 2 expansion cohorts.

Study enrollment and study treatment will be temporarily interrupted during dose escalation pending review of the following:

- Any death that is not related to disease progression occurring within 30 days of receiving investigational product.
- Occurrence of two grade \geq 4 DLTs in 2 study subjects.
- Any grade 4 hypersensitivity reaction/anaphylaxis.

Additional information regarding DESC responsibilities, membership requirements and safety review time points are described in [Section 10.4 Dose Escalation and Safety Committee] and further detailed in the DESC Charter.

4.1.5 Phase 2 (Dose Expansion)

Phase 2 will assess the safety and efficacy of ASP7517. This phase of the study may open once the RP2D and/or MTD are determined from the dose escalation phase, OR all of the following conditions are met before the RP2D and/or MTD determination.

- At least 1 subject in the dose escalation cohort (phase 1) achieves CRc for AML subjects, or CR, BM CR or PR for MDS subjects.
- The dose level to be expanded is deemed tolerable by the DESC.
- The dose that will be opened for expansion is determined to be equal or lower than the possible MTD.

Phase 2 will include the following groups and may enroll in parallel and independently:

- Subjects with R/R AML.
- Subjects with R/R higher risk MDS.

The CRc rate for subjects with R/R AML and CR + BM CR + PR rate for R/R higher risk MDS are continuously monitored using the Bayesian optimal phase 2 (BOP2) design [Zhou et al, 2017]. The number of dose levels investigated during phase 2 will be based upon the data from phase 1. Initially, 12 subjects will be enrolled at each dose level for each disease type during stage 1 of BOP2. If the response rate does not meet the optimal stopping boundaries (see table below), then stage 2 will open and an additional 20 subjects may be enrolled during this stage. Combining the data from stage 1 and stage 2, stage 3 may be opened for an additional 20 subjects for a total maximum sample size of 52 for each disease type, if the response rate does not meet the optimal stopping boundaries (see table below). Otherwise, the enrollment at that dose level will be closed.

When the total number of subjects reaches the maximum sample size of 52, it may be concluded that ASP7517 is efficacious if the number of responses is greater than or equal to 12 and 10 for AML and MDS, respectively. The number of subjects in stage 1, stage 2 and stage 3 may be changed according to the optimized stopping boundaries.

Optimized Stopping Boundaries for AML	
Number of subjects treated	Stop if number of responses ≤
12	1
32	5

AML: acute myeloid leukemia

Optimized Stopping Boundaries for MDS	
Number of subjects treated	Stop if number of responses ≤
12	0
32	4

MDS: myelodysplastic syndrome

Stopping Rules based on Safety for Phase 2

The stopping rules described below will be applied to both AML and MDS disease types.

The safety in phase 2 will be monitored using a Bayesian logistic model based on safety events including:

- All DLT data obtained at the time of the analysis from both escalation and expansion cohorts.
- Drug related treatment emergent AEs leading to death.

Safety monitoring with these models will start when phase 2 is opened. Enrollment in phase 2 will be stopped based on the following 2 criteria:

- If the posterior mean of the safety event rate is higher than 30% as indicated by Bayesian logistic model across disease types at a given dose level, then enrollment will be stopped in phase 2 at that dose level and at higher dose levels for that therapy.
- Additionally, if the posterior mean of the safety event rate is higher than 30% as indicated by Bayesian logistic model in a specific disease type at a dose level, enrollment of that dose level and any higher dose level will be stopped for that disease type.

4.1.6 Dose Rationale

The starting dose for the first in human (FiH) study is anticipated to be safe with minimal pharmacological activity, as supported by the nonclinical studies. The starting dose of ASP7517 is set to 1×10^6 cells/dose by intravenous infusion.

Nonclinical pharmacology data suggest ASP7517-surrogate shows prolonged survival when administered intravenously to a C1498-WT1 inoculated mouse AML model (per 30 g mouse), and prolonged survival was confirmed at the lowest dose level (5×10^2 cells/mouse) in the study. The dose of 5×10^2 cells/mouse is calculated as 1.7×10^4 cells/kg (5×10^2 cells/30 g); therefore, the starting dose is estimated to be 1×10^6 cells/dose (1.7×10^4 cells/kg \times 60 kg).

The starting dose was also assessed according to the results of the nonclinical toxicology studies. Toxicities (e.g., liver findings, changes in platelet count) were observed after ASP7517 intravenous administration at the lowest dose used in nonclinical studies (1×10^5 cells/kg; equivalent to 6×10^6 cells/dose, administered per 60 kg human), and the NOAEL was not established in the studies. However, these adverse effects are considered to be immune-related reactions based on the mechanism of action of ASP7517, and it is expected that the toxicities are reversible and monitorable in the nonclinical studies. Consequently, it is considered possible to set the starting dose for the FiH study as 1×10^6 cells/dose, 6-fold lower than the lowest dose of nonclinical toxicology studies, with careful clinical monitoring.

The dosing regimen for the FiH study is a total of up to 2 doses in the escalation phase and up to 6 doses in the expansion phase, one dose in each 28-day cycle, which is supported by nonclinical pharmacology data. In mice immunized with specific antigen expressing aAVC at day 0 and day 28, NKT cells and T cells were stimulated after first and second administration. Also, long term antigen-specific antitumor immune memory was demonstrated in an EG7 inoculated mouse model after single administration.

4.2 End of Study Definition

The study start is defined as the date the first subject signs the informed consent form (ICF). End of the study is defined as the last visit or scheduled procedure shown in the Schedule of Assessments for the last subject in the study.

Study completion is defined as the conclusion of data collection for the defined study endpoints. The study may be closed within a participating country per local regulations once the study has been completed and if all subjects enrolled in the country are no longer receiving IP.

5 STUDY POPULATION

Subjects with R/R AML or R/R higher risk MDS will be included.

All screening assessments must be completed and reviewed to confirm the potential subject meets all eligibility criteria. Prospective approval of protocol deviations to eligibility criteria (also known as protocol waivers or exemptions) is not permitted.

5.1 Inclusion Criteria

Subject is eligible for participation in the study if all of the following apply:

1. Institutional Review Board (IRB)/Independent Ethics Committee (IEC) approved written informed consent and privacy language as per national regulations (e.g., Health Insurance Portability and Accountability Act authorization [HIPAA] for US study sites) must be obtained from the subject or legally authorized representative prior to any study-related procedures (including withdrawal of prohibited medication, if applicable).
2. Subject is considered an adult according to local regulation at the time of signing the ICF.
3. Subject diagnosed with R/R AML or R/R higher risk MDS is defined as:
 - R/R AML
 - Morphologically documented primary or secondary AML by the WHO criteria (2016),
AND
 - Refractory to at least 2 cycles of induction chemotherapy/not a candidate for re-induction OR relapsed after achieving remission with a prior therapy,
AND
 - Received all standard therapies including targeted therapies (unless the therapy is contraindicated or intolerable) which are known to provide clinical benefit in the opinion of the investigator,
AND
 - Received salvage therapy OR is not a candidate for salvage therapy
 - R/R Higher Risk MDS
 - Has MDS by the WHO criteria (2016),
AND

- Either relapsed after achieving remission or refractory to standard therapies, including ≥ 4 cycles of hypomethylating agents (unless the therapy is contraindicated or intolerable),
AND
- Is classified as higher risk MDS with a score of > 3.5 by Revised International Prognostic Scoring System (IPSS-R) in MDS

4. Subject has an Eastern Cooperative Oncology Group (ECOG) performance status of ≤ 2 .
5. Subject must meet the following criteria as indicated on the clinical laboratory tests during screening period:
 - Serum AST and ALT $\leq 2.5 \times$ upper limit of normal (ULN)
 - Serum total bilirubin (TBL) $\leq 1.5 \times$ ULN
 - Serum creatinine $\leq 1.5 \times$ ULN or an estimated glomerular filtration rate of > 50 mL/min as calculated by the Modification of Diet in Renal Disease equation
 - Platelets $\geq 50,000/\mu\text{L}$ at cycle 1 day 1 (C1D1) in the dose escalation cohort only
6. Subject has a life expectancy of ≥ 12 weeks at the time of screening in the opinion of the investigator.
7. Subjects with AML must have peripheral blood absolute blast count of $< 20,000/\mu\text{L}$ at C1D1.

Note: Blast count can be controlled by hydroxyurea during screening period.
8. Female subject is not pregnant [see Appendix 12.3 Contraception Requirements] and at least 1 of the following conditions apply:
 - Not a woman of childbearing potential (WOCBP) [see Appendix 12.3 Contraception Requirements]
 - WOCBP who agrees to follow the contraceptive guidance [see Appendix 12.3 Contraception Requirements] from the time of informed consent through at least 180 days after final study treatment administration
9. Female subject must agree not to breastfeed starting at screening and throughout the study period and for 180 days after the final study treatment administration.
10. Female subject must not donate ova starting at first dose of IP and throughout the study period and for 180 days after final study treatment administration.
11. Male subject with female partner(s) of childbearing potential (including breastfeeding partner) must agree to use contraception [see Appendix 12.3 Contraception Requirements] throughout the treatment period and for 180 days after final study treatment administration.
12. Male subject must not donate sperm during the treatment period and for 180 days after the final study treatment administration.

13. Male subject with pregnant partner(s) must agree to remain abstinent or use a condom for the duration of the pregnancy throughout the study period and for 180 days after final study treatment administration.
14. Subject agrees not to participate in another interventional study while receiving study treatment in the present study.

Waivers to the inclusion criteria will **NOT** be allowed.

5.2 Exclusion Criteria

Subject will be excluded from participation in the study if any of the following apply:

1. Subject was diagnosed with acute promyelocytic leukemia.
2. Subject has breakpoint cluster region-Abelson-positive leukemia (BCR-ABL).
3. Subject has persistent non-hematological toxicities of \geq grade 2 (National Cancer Institute's Common Terminology Criteria for Adverse Events [NCI-CTCAE], version 5.0), with symptoms and objective findings from prior AML or MDS treatment (including chemotherapy, kinase inhibitors, immunotherapy, experimental agents, radiation or surgery).
4. Subject has received any of the following therapies:
 - Systemic immunomodulators or immunosuppressive drugs including steroids \leq 28 days prior to C1D1 (steroids can be used if not intended for treatment of AML or MDS; steroids for AML/MDS related symptoms can be used at low doses [less than 10 mg/day dexamethasone])
 - Cytotoxic agents (except hydroxyurea given for controlling blast cells) \leq 28 days prior to C1D1
 - IPs for the treatment of AML or MDS within 5 half-lives prior to screening visit
 - HSCT
 - Radiation therapy \leq 28 days prior to C1D1
5. Subject has clinically active nervous system leukemia, per the investigator's judgment.
6. Subject has active or prior documented autoimmune or inflammatory disorders requiring systemic treatment.
7. Subject has ongoing, untreated malignancy with the exception of the following:
 - Subjects with treated non-melanoma skin cancer, in situ carcinoma or cervical intraepithelial neoplasia, regardless of the disease-free duration, are eligible for this study if definitive treatment for the condition has been completed.
 - Subjects with organ-confined prostate cancer with no evidence of recurrent or progressive disease are eligible if hormonal therapy has been initiated or the malignancy has been surgically removed or treated with definitive radiotherapy.
8. Subject with left ventricular ejection fraction of $< 45\%$ on echocardiogram (ECHO) or multigated acquisition scan (MUGA) performed within 28 days of screening.

9. Subject has laboratory abnormalities or clinical evidence of disseminated intravascular coagulation, or ongoing history of coagulation disorder manifested by bleeding or clotting.
10. Subject has an active uncontrolled infection.
11. Subject is known to have human immunodeficiency virus infection.
12. Subject has active hepatitis B or C or other active hepatic disorder.
13. Subject has any condition, which in the investigator's opinion, makes the subject unsuitable for study participation.
14. Subject has a known or suspected hypersensitivity to bovine-derived protein or has suspected hypersensitivity to any ingredients of ASP7517.
15. Subject is eligible for HSCT.

Waivers to the exclusion criteria will **NOT** be allowed.

5.3 Restrictions During The Study

Not applicable.

5.4 Screen Failures

A screen failure is defined as a potential subject who signed the ICF but did not meet 1 or more criteria required for participation in the study and was not enrolled.

For screen failures, the demographic data, date of signing the ICF, inclusion and exclusion criteria, AEs up to the time of screen failure and reason for screen failure will be collected in the electronic case report form (eCRF).

5.4.1 Rescreening

Results of screening assessments that do not meet the parameters required by eligibility criteria (e.g., clinical laboratory tests, vital signs, physical examination, electrocardiogram [ECG], etc.) may be repeated once within the 14-day screening period without the need to register the subject as a screen failure. If more than 14 days elapse from the date of signing the ICF, the subject must be documented as a screen failure. In order to rescreen, a new ICF must be signed and the subject must be entered into screening with a new subject identification number. Rescreening is only allowed once for an individual subject. The bone marrow sample and ECHO/MUGA screening assessments completed within 28 days prior to first dose do not need to be repeated.

6 INVESTIGATIONAL PRODUCT

6.1 Investigational Product Administered

Table 8 Investigational Product

Name	ASP7517
Dosage Formulation	Suspension for injection
Physical Description	Opalescent and white to slightly yellowish-white suspension
Unit Dose Strength	1×10^7 cells/mL
Packaging and Labeling	Clear single use vial
Route of Administration	Intravenous infusion
Administration Instruction	Fifty (50) mL of diluted IP will be administered by intravenous infusion at 4 to 6 mL/min infusion rate through a dedicated intravenous line, followed by flushing
IMP or Non-IMP	IMP
Storage	-150°C or below
Sourcing	Provided centrally by sponsor

IMP: Investigational Medicinal Product.

Refer to the pharmacy manual for detailed information regarding preparation, handling and storage of the IP.

6.1.1 Administration

ASP7517 will be infused in 50 mL of normal saline solution at 1×10^6 , 1×10^7 , or 1×10^8 total cells/dose. It will be administered by intravenous infusion with an infusion rate between 4 to 6 mL/min through a dedicated intravenous line, followed by flushing.

Refer to the pharmacy manual for detailed information regarding administration of the IP.

6.2 Preparation/Handling/Storage/Accountability

6.2.1 Packaging and Labeling

All IP used in this study will be prepared, packaged and labeled under the responsibility of qualified personnel at Astellas Pharma Global Development Inc. (APGD) or sponsor's designee in accordance with APGD or sponsor's designee standard operating procedures (SOPs), Good Manufacturing Practice (GMP) guidelines, International Council for Harmonisation of Technical Requirements for Pharmaceuticals for Human Use (ICH) Good Clinical Practice (GCP) guidelines and applicable local laws/regulations. The intravenous infusion will be prepared onsite by a pharmacist or qualified person using aseptic technique as specified in the pharmacy manual.

Each vial will bear a label conforming to regulatory guidelines, GMP and local laws and regulations that identifies the contents as investigational drug.

Refer to the pharmacy manual for detailed information regarding packaging and labeling of the IP.

6.2.2 Handling, Storage and Accountability

- The investigator or designee must confirm appropriate temperature conditions have been maintained during transit for all IP received and any discrepancies are reported and resolved before use of the IP.
- Only subjects enrolled in the study may receive IP and only authorized study site personnel may supply or administer IP. Only IP with appropriate expiry/retest dating may be dispensed.
- All IP must be stored in a secure, environmentally controlled and monitored (manual or automated) area in accordance with the labeled storage conditions and access must be limited to the investigator and authorized study site personnel.
- The investigator, institution or the head of the medical institution (where applicable) is responsible for accountability, reconciliation and record maintenance (i.e., receipt, reconciliation and final disposition records).
- Further guidance and instruction on final disposition of used and unused IP is provided in the pharmacy manual.

Refer to the pharmacy manual for detailed information regarding IP handling, storage and accountability of the IP.

6.3 Randomization and Blinding

This is an open-label study. Subject enrollment and dispensation of IP will be performed via the interactive response technology (IRT) system. Specific IRT procedures will be described in the respective study manual.

6.3.1 Assignment and Allocation

Priority for enrollment will be given to the phase 1 dose escalation portion before phase 2 dose expansion.

For phase 2 enrollment, if more than 1 dose level is open for enrollment within a selected disease type, the newly enrolled subjects with that disease type will be randomly allocated to 1 of the open dose levels. Randomization will be weighted towards newly opened dose levels, with the allocation ratio based on the number of open slots still available at each dose level. For example, if dose level 'x' enrolled 3 subjects and dose level 'y' is newly opened for expansion, the next subject would be randomly allocated to dose level 'x' or 'y' with the ratio of 9:12.

When escalation and expansion cohorts are both open for enrollment, enrollment into escalation cohorts takes priority such that subjects who are eligible for both will be preferentially enrolled in the escalation cohorts.

6.4 Investigational Product Compliance

Dosing will take place in the clinical unit. The administration of IP will be supervised to ensure treatment compliance. The exact day and time of IP administration will be documented.

6.5 Previous and Concomitant Treatment (Medication and Nonmedication Therapy)

The following treatments are prohibited during the study:

- Interferon/polyethylene-interferon
- High-dose systemic corticosteroids with the exception for immune-related AEs
- Immunosuppressive agents
- Investigational agents other than ASP7517
- Any other treatments of AML or MDS (including but not limited to chemotherapy, radiotherapy, surgery, immunotherapy or cellular therapy) are prohibited during the study with ASP7517 with the following exceptions:
 - Hydroxyurea up to 5 g daily for up to 2 weeks to keep the absolute blast count < 20,000/ μ L
 - Subject undergoing HSCT will be discontinued from the study
 - Intrathecal chemotherapy used as prophylaxis

Refer to [Appendix 12.6 List of Excluded Concomitant Medications] for a detailed list of drug classes and/or specific medications that are prohibited during participation in the study.

6.6 Dose Modification

Dose modifications are not allowed. Any subjects who do not receive a subsequent dose within the scheduled time window in the Schedule of Assessments [Table 1 and Table 2] can only resume treatment after discussion with the medical monitor. Any subject experiencing a grade 3 AE related to IP after receiving a dose of ASP7517 may receive the subsequent scheduled dose of ASP7517 only after the observed grade 3 AE has resolved to grade 1; the subsequent dose of ASP7517 may be reduced to a dose level deemed safe by the DESC. Further treatment reduction/withdrawal can be implemented after discussion with the medical monitor, including for any clinically significant AEs affecting vital organs (e.g., cardiac events).

6.7 Criteria for Continuation of Treatment

ASP7517 will not be made available after conclusion of the study to subjects who are still receiving and benefitting from study treatment in countries where the product does not have marketing approval and is not commercially available. ASP7517 is given as a maximum of 6 doses (up to 2 doses in the escalation phase; up to 6 doses in the expansion phase).

7 STUDY PROCEDURES AND ASSESSMENTS

7.1 Efficacy Assessments

7.1.1 Response Criteria Definitions

7.1.1.1 Acute Myeloid Leukemia Response Criteria

Response to treatment will be defined per modified criteria [Cheson et al, 2003] as outlined below.

- Complete Remission (CR)

For subjects to be classified as being in CR at a post-baseline visit, they must have bone marrow regenerating normal hematopoietic cells and achieve a morphologic leukemia-free state and must have an absolute neutrophil count (ANC) $\geq 1 \times 10^9/L$ and platelet count $\geq 100 \times 10^9/L$, and normal marrow differential with $< 5\%$ blasts, and they will be red blood cell (RBC) and platelet transfusion independent (defined as 1 week without RBC transfusion and 1 week without platelet transfusion). There must be no presence of Auer rods. There should be no evidence of extramedullary leukemia. The blast counts in peripheral blood must be $\leq 2\%$.

- Complete Remission with Incomplete Platelet Recovery (CRp)

For subjects to be classified as being in CRp at a post-baseline visit, they must achieve CR except for incomplete platelet recovery ($< 100 \times 10^9/L$).

- Complete Remission with Incomplete Hematological Recovery (CRI)

For subjects to be classified as being in CRI at a post-baseline visit, they must fulfill all the criteria for CR except for incomplete hematological recovery with residual neutropenia (ANC $< 1 \times 10^9/L$) with or without complete platelet recovery. RBC and platelet transfusion independence is not required.

- Composite Complete Remission (CRC)

For subjects to be classified as being in CRC at a post-baseline visit, they must either achieve CR, CRp or CRI at the visit.

- Complete Remission with Partial Hematologic Recovery (CRh)

For subjects to be classified as CRh at a post-baseline visit, if they have marrow blasts $< 5\%$, partial hematologic recovery ANC $\geq 0.5 \times 10^9/L$ and platelets $\geq 50 \times 10^9/L$, no evidence of extramedullary leukemia and cannot be classified as CR. The blast counts in peripheral blood must be $\leq 2\%$.

- Partial Remission (PR)

For subjects to be classified as being in PR at a post-baseline visit, they must have bone marrow regenerating normal hematopoietic cells with evidence of peripheral recovery with no (or only a few regenerating) circulating blasts and with a decrease of at least 50% in the percentage of blasts in the bone marrow aspirate with the total marrow blasts between 5% and 25%. A value of less or equal than 5% blasts is also considered a PR if Auer rods are present. There should be no evidence of extramedullary leukemia.

- Not Evaluable (NE)/No Response (NR)

In the situation where no bone marrow assessments are performed or myeloblast value is missing, blast value from peripheral blood is missing or $\leq 2\%$, and extramedullary leukemia is missing or not present, the response will be classified as NE. In any case response cannot be categorized as CR, CRp, CRI, PR or NE, it will be categorized as NR.

- Relapse

Relapse after CR, CRh, CRp or CRi is defined as a reappearance of leukemic blasts in the peripheral blood ($> 2\%$) or $\geq 5\%$ blasts in the bone marrow aspirate not attributable to any other cause or reappearance or new appearance of extramedullary leukemia.

Relapse after PR is similarly defined with reappearance of significant numbers of peripheral blasts and an increase in the percentage of blasts in the bone marrow aspirate to $> 25\%$ not attributable to any other cause or reappearance or new appearance of extramedullary leukemia.

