**Table 1 Response Classification Schema for AML**

Myeloblast in Bone Marrow Aspirate/Biopsy	Blast in Peripheral Blood	Extramedullary Leukemia	Auer Rod	RBC Transfusion	Platelet Transfusion	ANC	Platelet	Response
<5%	Missing or <=2%	Absent/Missing	Absent/Missing	No	No	$\geq 1 \times 10^9/L$	$\geq 100 \times 10^9/L$	CR
<5%	Missing or <=2%	Absent/Missing	Absent/Missing	No	No	$\geq 1 \times 10^9/L$	< 100 $\times 10^9/L$	CR p
<5%	Missing or <=2%	Absent/Missing	-	-	-	$\geq 0.5 \times 10^9/L$	$\geq 50 \times 10^9/L$	CR h
<5%	Missing or <=2%	Absent/Missing	Absent/Missing	-	-	-	-	CR i
>=5% - <=25% and >=50% decrease from baseline	Missing or <=2%	Absent/Missing	-	-	-	-	-	PR
<5%	Missing or <=2%	Absent/Missing	Present	-	-	-	-	PR
Missing	Missing or <=2%	Absent/Missing	-	-	-	-	-	NE
Any case that cannot be categorized as CR, CR p , CR h , CR i , PR, or NE								NR

- Relapse
  - Relapse after CR, CRh, CRp or CRI is defined as a reappearance of leukemic blasts in the peripheral blood (> 2%) or  $\geq 5\%$  blasts in the bone marrow aspirate not attributable to any other cause or reappearance or new appearance of extramedullary leukemia.
  - Relapse after PR is similarly defined with reappearance of >2% of peripheral blasts and an increase in the percentage of blasts in the bone marrow aspirate to > 25% not attributable to any other cause or reappearance or new appearance of extramedullary leukemia.
- Best Response
  - Best response is defined as the best measured response to treatment for all visits (in the order of CR, CRp, CRI, PR, NR and NE) post-baseline. Subjects who achieve the best response of CR, CRp, CRI or PR will be classified as responders. Subjects who do not achieve at least a best response of PR will be considered non-responders.
- MDS
  - Complete Remission (CR): For subjects to be classified as being in CR at a post-baseline visit, they must have all of the following maintained for a minimum of 4 weeks:
    - Bone marrow evaluation:  $\leq 5\%$  myeloblasts with normal maturation of all cell lines
    - Peripheral blood evaluation:
      - Hemoglobin  $\geq 11$  g/dL
      - Platelets  $\geq 100 \times 10^9$  /L
      - Neutrophils  $\geq 1.0 \times 10^9$ /L
      - 0% blasts in blood
  - Partial Remission (PR): For subjects to be classified as being in PR at a post-baseline visit, they must have all CR criteria if abnormal before treatment except the following for a minimum of 4 weeks:

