### **5.1.4 Secondary Efficacy Endpoint: CR/CRh Rate**

CR/CRh rate is defined as the number of subjects who achieve CR or CRh at any of the postbaseline visits divided by the number of subjects in the analysis population. CR/CRh is applicable for AML subjects only.

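### CRh has no Auer-rod exclusion, so a marrow that the same section classes as PR also counts in the CRh and CR/CRh rates

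*Protocol*

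**What the plan says.** Protocol 7.1.1.1 builds CR, CRp and CRi on one set of conditions. For CR it states: "There must be no presence of Auer rods". CRp is CR apart from platelet recovery, and CRi is CR apart from hematological recovery, so both carry the Auer-rod condition by reference.

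CRh is defined separately. It requires marrow blasts below 5%, ANC at least 0.5 × 10^9/L, platelets at least 50 × 10^9/L and peripheral blasts of at most 2%, with "no evidence of extramedullary leukemia and cannot be classified as CR". There is no Auer-rod term and no reference back to the CR conditions beyond not being CR.

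The PR definition that follows adds a low-blast route: "A value of less or equal than 5% blasts is also considered a PR if Auer rods are present".

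SAP 5.1.1 repeats these definitions. Its Table 1, "Response Classification Schema for AML", shows Absent/Missing under Auer Rod for CR, CRp and CRi, and a dash for CRh. A separate row gives PR for blasts below 5% with Auer rods present.

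CRh then feeds two rates. In SAP 5.1.4, "CR/CRh rate is defined as the number of subjects who achieve CR or CRh at any of the postbaseline visits", and SAP 5.1.3 defines the CRh rate in the same way. Protocol 9.4.2 matches both.

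**The concern.** The plan treats Auer rods as incompatible with every category inside CRc, and as the feature that turns an otherwise low-blast marrow into PR. CRh is the only remission category without that bar. A visit that misses CR solely because Auer rods were seen meets the requirement of not being CR, so the failure itself lets it qualify as CRh.

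At stake is the meaning of two AML secondary endpoints, the CRh rate and the CR/CRh rate. Both count a subject on one qualifying post-baseline visit. As written, they can include subjects whose marrow the protocol itself calls partial remission, and two programmers following the plan could classify the same visit differently.

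**Working it through.** The documents give no figure for this point to reproduce. The check sets the definitions side by side, applies them to a visit, counts the overlap and sizes one subject.

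**1. Auer-rod condition by category**

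| Category | Text (Protocol 7.1.1.1, SAP 5.1.1) | Auer Rod cell, SAP Table 1 |
|---|---|---|
| CR | must be absent | Absent/Missing |
| CRp | absent, by reference to CR | Absent/Missing |
| CRi | absent, by reference to CR | Absent/Missing |
| CRh | no term | dash |
| PR, low-blast route | present | Present |

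**2. One visit put through the text.** Take a regenerating marrow with 3% blasts and Auer rods present, ANC 1.2 and platelets 120 (× 10^9/L), no transfusion in the past week, peripheral blasts at most 2% and no extramedullary leukemia.

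- CR: fails, on Auer rods alone.
- CRp and CRi: fail, because both carry the Auer-rod condition.
- CRh: met, since 3 < 5, 1.2 ≥ 0.5, 120 ≥ 50 and the visit is not CR.
- PR: met, since 3 ≤ 5 with Auer rods present.

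**3. How far the overlap extends.** Fix marrow blasts below 5%, peripheral blasts at most 2% and no extramedullary leukemia. Cross Auer rods (2 levels), transfusion in the past week (2), ANC (below 0.5, 0.5 to 1, at least 1) and platelets (below 50, 50 to 100, at least 100): 2 × 2 × 3 × 3 = 36 patterns.

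- Patterns with ANC ≥ 0.5 and platelets ≥ 50: 2 × 2 × 2 × 2 = 16. One is CR, so 16 − 1 = 15 meet CRh.
- Of these, 2 × 2 × 2 = 8 have Auer rods present, and all 8 meet the low-blast PR sentence.
- With an Auer-rod exclusion, 15 − 8 = 7 CRh patterns remain, none of them PR by that sentence.

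These are counts of definition patterns, not patient rates. The overlap stops below 5%: a marrow at exactly 5% with Auer rods is PR only.

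**4. Whether the plan resolves it.** The best-response order for AML (Protocol 9.4.2, SAP 5.1.5) is CR, CRp, CRi, PR, NR, NE. CRh is not in it, so the visit is PR there while still counting in the CRh and CR/CRh rates. Table 1 states no reading order. If its rows are read from the top, CRh stands above the Auer-rod PR row and takes the visit.

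**5. Size per subject.** For a subject whose only qualifying visits are Auer-rod positive, the step in the rate is 1/n:

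- Full AML cohort at one dose level, n = 52: 1/52 = 1.9 percentage points.
- After stage 2, n = 32: 1/32 = 3.1 percentage points.

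**The case against.** The best reply is that CRh is deliberately kept outside the best-response hierarchy and overlaps other categories by design. A visit with ANC 1.2, platelets 60, no Auer rods and no transfusion is both CRp and CRh, and nobody would call that an error. This is fair, and overlap alone is not the complaint. The difference is that CRp is itself a complete-remission category. The Auer-rod overlap joins a complete-remission label to a marrow that the section assigns to PR, and nothing in the documents indicates that this was intended.

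A second reply is that little depends on it. Best response rate does not change when the visit is taken as PR, because PR is already a response. No decision rule uses CRh, and SAP 6.4.2.5 presents duration of response in a listing only. All of that stands and limits the weight of the point.

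A reader might also infer that CRh wrongly lacks a transfusion condition. CR requires transfusion independence ("defined as 1 week without RBC transfusion and 1 week without platelet transfusion"), and without such a rule a transfused platelet count can meet the limit of 50. The documents do not support calling this an error. Protocol text, SAP text and Table 1 agree in setting no transfusion condition for CRh. Table 1 uses the same dashes for CRi, where the text says that "RBC and platelet transfusion independence is not required". No section says that CRh must be transfusion-free. A sentence confirming the intent would help, but imposing the one-week rule would be a preference.

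**Conclusion.** The point holds for Auer rods. CRh as defined in both documents admits a marrow that the same section classes as PR, and no rule decides between the two. The CRh and CR/CRh rates can be raised by 1.9 points per affected subject at n = 52, or 3.1 points at n = 32. This assumes that every subject in the cohort is in the denominator and that the affected subject has no other visit qualifying for the rate.

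The total effect cannot be computed. The documents give no frequency of Auer rods in marrows below 5% blasts, and any assumed number of affected subjects would have no source in them.

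A reader might infer that the primary result or the design is compromised. It is not. CRc consists of CR, CRp and CRi, all of which exclude Auer rods when they are recorded as present, and the BOP2 design monitors CRc. The boundaries and stated power are therefore untouched. Nor do the documents show a biased duration estimate, since the SAP plans none. This is a definition to correct in secondary endpoints.

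**What to change.** Add to the CRh definition, in Protocol 7.1.1.1 and SAP 5.1.1, the Auer-rod exclusion that CR already carries. In SAP Table 1, change the Auer Rod cell of the CRh row from a dash to Absent/Missing. An Auer-rod-positive marrow below 5% blasts then falls only to PR, and no separate precedence rule is needed for this overlap.

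The cell should not read Absent alone. The CR, CRp and CRi rows accept a missing result, so that setting would make CRh stricter than CR on this item. Auer rods are not named among the bone marrow parameters in Protocol Table 12 or SAP Table 5, so missing results are plausible.

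The cost is one line in each document and one table cell, using an item that the CR derivation already refers to. The CRh and CR/CRh rates may come out slightly lower.
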